8.4 Inclusion and exclusion criteria

Inclusion criteria: 1. Patients admitted to the Centro Medico ISSEMYM Toluca Arturo Montiel Rojas, diagnosed with COVID-19. 2. Patients in need of supplemental O₂ with nasal prongs or mask-reservoir due to satO₂ <90% and respiratory distress. 3. With concomitant diseases such as cardiovascular disease, diabetes mellitus 2, hypertension, overweight or obesity BMI <35. 4. 5. Over 30 years of age. 6. Tolerant of oral feeding. 7. Signed informed consent letter.

Non-inclusion criteria: 1. Who requires mechanical ventilatory support. 2. 2. Present neurological or neurodevelopmental disorders. Severe gastroesophageal reflux and/or dysphagia. 4. 4. Patients with any type of surgery performed in a period of less than 3 months. 5. Allergies to any ingredient of the study treatment. 6. Who present acute malnutrition. 7. Patients who require admission to the Intensive Care Unit. 8. Who has criteria of sepsis or septic shock. 9. Glomerular filtration rate less than 60ml/min/1.73m².

Criteria for elimination: 1. Treatment failure. 2. Admission to ICU for any reason. 3. Patients who do not tolerate the oral route. 4. Reactions to treatment that compromise the health of the patients.

Sampling and allocation: Consecutive cases. Systematic randomized allocation by means of a sequence of random numbers constructed with the Excel program divided into two groups.

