Item 13b: Any planned adjustment of the significance level due to interim analysis:

No adjustment of the significant level due to interim analysis are planned.

13c. Details of guidelines for stopping a trial early:

The following points are considered in planning the early stopping of the study:

1. That the intervention causes serious adverse effects in patients generating insecurity in its application.
2. That the investigators detect improbable, ineffective, or extreme differences between the CG and the IG.

3. New information emerges that raises serious safety issues or convincingly answers to the main question.

14. Timing of final analysis

Item 14: Timing of final analysis e.g all outcome analyzed collectively or timing stratified by planned length of follow-up

The follow-up will start in September 2020 until the established sample is met.

The last day of the study for each patient is going to be 40 days after hospital discharge.

Statistical analysis of clinical and biochemical variables will be performed on baseline, day three, hospital discharge and day 40. Analysis of overall survival and mortality will be performed from baseline to day 40 or patient death. Progression of patients to Mechanical Ventilation Assistance (MVA) will be performed from baseline until the last patient is intubated, mortality in patients with MVA will be performed from intubation to day 40 or death.

15. Timing of outcome assessments

Item 15: Time points at which the outcomes are measured

Survival and Mortality

- Overall survival and mortality: performed from baseline to day 40 or patient death.
- Progression of patients to Mechanical Ventilation Assistance (MVA): performed from baseline until the last patient is intubated.
- Mortality in patients with MVA: performed from intubation to day 40 or death.

Clinical and biochemical variables

- Delivered oxygen flow and maintenance of SpO₂ > 90%: will be analyzed at baseline and day three.
- qSOFA scale: will be analyzed at baseline compared with day three.

- Gastrointestinal function (average of gastrointestinal movements, abdominal distension, and Bristol scale): will be analyzed at baseline compared with day three.
- Laboratory parameters: will be analyzed at baseline, day three and hospital discharge.
- PHQ-9: will be analyzed at baseline and hospital discharge.

Follow-up at day 40

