- SpO2 without supplemental oxygen, use of home oxygen upon hospital discharge, days of supplemental oxygen use, post-covid syndrome, decrease in body weight: all will be analyzed from hospital discharge until day 40.

Section 4: Statistical Principles

16. Confidence intervals and p-values

Item 16: Level of statistical significance

P values ≤ 0.05 will be considered indicative of statistical significance in all cases. P values will be one-sided.

Item 17: Description of any planned adjustment for multiplicity, and if so, including how the type I error is to be controlled

This study will not analyze data that required multiplicity tests. To avoid type 1 error, an alpha value of 5% will be used (considering $p < 0.05$ significant), aberrant data will be eliminated, validated tests applicable to the study variables will be defined and established, specific inclusion criteria will be implemented for homogenization of the sample to avoid bias variables, and a specific sample size calculation will be performed.

Item 18: Confidence intervals (CI) to be reported

All the confidence intervals presented will be 95%.

19. Adherence and Protocol Deviations

Item 19a: Definition of adherence to the intervention and how this is assessed including extent of exposure.

The intervention will consist of: 1) 2 envelopes of NSS taken in a period of less than 15 minutes (without the presence of vomiting) after morning and afternoon meals during the first 21 days or until hospital discharge, 2) 1 capsule of *Saccharomyces Boulardii* before the NSS and 1 capsule with the second envelope for 6 days or until hospital discharge, 3) intramuscular B complex; 1 ampoule after meals for 5 days or at hospital discharge.

Adherence to treatment will be established as taking more than 95% of the NSS and not fasting for 2 consecutive days.

Item 19b: Description of how adherence to the intervention will be presented

The intervention will be applied by the research team, who will be responsible for the application and collection of data, which will be reported in daily formats in the morning and afternoon shifts.

The clinical investigators are going to prepare each supplement, administer, and witness each intake of the NSS, registering the time as well as any immediate side effects such as vomiting, bloating, and abdominal pain.

Item 19c: Definition of protocol deviation for the trial:

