Categorical data will be summarized by numbers and percentages. Normality tests will be applied to evaluate the distribution of the data. If the continuous data present a normal distribution, they will be assumed by mean, SD, and range. If they do not present a normal distribution, they will be summarized with the median and the IQR. Minimum and maximum values will also be presented for continuous data. Statistical significance tests will be performed between both groups in the baseline to rule out significant differences.

Section 6: Analysis

26. Outcomes definitions

Item 26a: Specification of outcomes and timings

Primary outcomes

- Overall mortality and survival will be assessed from the baseline to day 40.
- Progression to AVM will be assessed from baseline until the last patient is intubated.
- Mortality and survival in intubated patients will be assessed from baseline to day 40.

These results will be included in the results section of the manuscript.

Secondary Outcomes

Administration of supplemental oxygen flow, oxygen saturation (spO₂), qSOFA scale, and gastrointestinal function will be assessed by comparing at baseline to day 3 intragroup and intergroup. The PHQ-9 test will be assessed at baseline and at discharge between both groups.

These results will be included in the secondary outcomes section of the manuscript. Analysis of the association of baseline biochemical parameters and mortality will be considered in a table and in the secondary outcomes section of the manuscript.

The spO₂ without supplemental oxygen requirement, home supplemental oxygen requirement, post COVID syndrome, and body weight at day 40 will be analyzed between both groups in a table.

These results are included in the follow-up section of the manuscript.

Item 26b: Specific measurement and units

- SpO₂ (%)
- Mortality (days of death)
- Kilocalories (kcal / day)
- PHQ9 (pts).
- Temperature (°C).
- Hemoglobin (g / dL).
- Mean corpuscular volume (fL).
- Mean corpuscular hemoglobin concentration (g / dL).
- Leukocytes ($10^3 / \mu\text{L}$).
- Neutrophils (%).
- Platelets ($10^3 / \mu\text{L}$).
- Glucose (mg / dL).
- Total cholesterol (mg / dL).
- Triglycerides (mg / dL).
- Aspartate aminotransferase (U / L).
- Alanine aminotransferase (U / L).
- Albumin (g/dL).
- Blood Urea Nitrogen (mg / dL).
- Urea (mg / dL).
- Creatinine (mg / dL).
- Glomerular filtration rate
- Ferritin (ng / mL)
- Fibrinogen (mg / dL)
- C-reactive protein (mg / L)
- Dimer-D (ng / mL)

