Risk factors and coexisting conditions – (%)			
Overweight	38 (95%)	36 (90%)	0.338
Obesity	14 (35%)	13 (32.5%)	1
DM 2	13 ± 0.325	11 ± 0.275	0.404
Cardiovascular disease	17 (42.5%)	10 (25%)	0.078
Hyperlipidemia	11 (27.5%)	7 (17.5%)	0.422
Gastrointestinal Disease	14 (35%)	13 (32.5%)	1
Total Risk Factors	2.92 ± 1.42	2.57 ± 1.35	0.261
Covid-19 Symptoms			
Dyspnea	24 (60%)	26 (65%)	0.409
Nausea and vomit	6 (15%)	7 (17.5%)	0.5
Hyposmia	12 (30%)	15 (37.5%)	0.637
Dysgeusia	18 (45%)	20 (50%)	0.412
Headache	26 (65%)	29 (72.5%)	0.315
Myalgia	32 (80%)	30 (75%)	0.395
Diarrhea	18 (45%)	12 (30%)	0.124
Anorexia	20 (50%)	21 (52.5%)	0.500
Total of symptoms	7.05 ± 2.11	6.8 ± 2.23	0.608
Gastrointestinal Clinic			
Bristol	9 (50%)	5 (27.8%)	0.153
Number of defecations	0.54 ± 0.6	0.52 ± 0.73	0.717
Abdominal distension	28 (70%)	28 (70%)	0.596
Vital Signs			
Breathing Frequency - bpm	21.18 ± 3.01	21.48 ± 3.01	0.378
Oxygen Saturation - %	92.73 ± 4.17	94 ± 3.18	0.144
Heart Rate - bpm	70.7 ± 15.4	75.5 ± 9.88	0.105
Temperature – °C	36.27 ± 0.73	36.3 ± 0.62	0.935
Oxygen flow – L/min	5.9 ± 3.82	6 ± 3.29	0.571
qSOFA - pts	0.425 ± 0.59	0.65 ± 0.62	0.100

SD, Standard Deviation. CG, control group. IG, intervention group.

Table 1-B. Clinical characteristics and baseline parameters of CG and IG.

Characteristics	CG	IG	P - value
	Mean (SD / %) n = 40	Mean (SD / %) n = 40	
Nutritional Status			
MNA® - pts	11.13 ± 2.26	11.38 ± 1.65	0.828
BMI – kg/m ²	29.35 ± 3.89	29.98 ± 4.07	0.403
Hydric balance – mL/day	-203.4 ± 966	-301.5 ± 1167	0.806
Medication			
Antihypertensive	13 (32.5%)	9 (22.5%)	0.227
Antidiabetics	9 (22.5%)	11 (27.5%)	0.398
Antilipids	3 (7.5%)	3 (7.50%)	0.662
Antibiotics	1 (2.50%)	4 (10%)	0.359
Antiacids	6 (15%)	6 (15%)	0.662
NSAIDs	8 (20%)	12 (30%)	0.220
Laboratory studies			
Hb – g/dL	15.53 ± 2.222	15.54 ± 2.088	0.987
MCHC – g/dL	33.39 ± 1.4	33.46 ± 1.17	0.753
Platelets – 10 ³ /μL	222.2 ± 53.93	248.4 ± 139.9	0.790
Leukocytes - 10 ³ /μL	8.97 ± 4.15	8.46 ± 4.36	0.400
Neutrophils - %	83.5 ± 8.87	80.78 ± 9.29	0.172
Glycemia – mg/dL	135.4 ± 59.39	134.8 ± 58.83	0.872
Total cholesterol – mg/dL	142.8 ± 42.82	135 ± 23.53	0.335
Triglycerides – mg/dL	147.5 ± 58.92	132.8 ± 37.39	0.533
AST – U/L	48.06 ± 28.81	46.4 ± 49.65	0.214
ALT – U/L	47.69 ± 31.9	50.44 ± 50.88	0.914
Albumin – g/dL	3.53 ± 0.44	3.57 ± 0.41	0.768
Ferritin – ng/mL	1070 ± 899.3	1270 ± 1142	0.572
Fibrinogen – mg/dL	592.2 ± 170.4	607.4 ± 162.9	0.721
CRP – mg/dL	157.3 ± 106.7	135.3 ± 94.92	0.313

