Clinical Evolution	CG				IG				Intergroup p-value
	n	Baseline	Day 3	P value	n	Baseline	Day 3	P value	
Oxygen flow - L (intragroup)	40	5.9 ± 3.8	6 ± 4.4	0.919	40	6 ± 3.2	4.5 ± 3.5	0.014 *	
qSOFA - pts	40	0.42 ± 0.59	0.51 ± 0.57	0.608	40	0.65 ± 0.62	0.43 ± 0.49	0.040 *	
Number of defecations on day 3	37		0.81 ± 0.90		36		1.41 ± 1.13		0.014 *
Distension on day 3	31		51.60%		31		19.40%		0.008 *
PHO-9 test – pts (intragroup)	6	3.66 ± 2.5	1.50 ± 2.8	0.187	10	5.3 ± 3.4	1.9 ± 1.4	0.003 *	
Oxygen Saturation >90% on day 3 -%	40		85%		40		92.50%		0.241
Hydric Balance on day 3 - mL	17		123.4 ± 453.8		18		456.6 ± 485.5		0.043 *
Bristol scale on day 3 - %	24		33.30%		31		41.90%		0.356
40-day follow-up			Day 40				Day 40		
Saturation without Supplementary Oxygen - %	28		90.39 ± 3.4		38		92.08 ± 2.5		0.030 *
Need for home Oxygen flow - %	27		85.2%		39		66.70%		0.078
Time of home Oxygen use – days	17		57.6 ± 24.6		23		43.8 ± 16.2		0.098
Post-covid syndrome - %	24		37.50%		34		23.50%		0.195
Weight decrease - % of patients	11		72.70%		18		44.40%		0.135
Gastrointestinal symptoms - %	24		16.70%		37		8.10%		0.266

Table 2-A The following table shows the results of the intergroup analysis between the IG (Intervention Group) and the CG (Control Group) for different parameters in the baseline or with a complete 40-day follow-up. Deceased patients were excluded. * p-value <0.05.

Table 2-B. Association of baseline laboratory parameters and general mortality.

Baseline values	Discharge (n=72)		Death (n=8)		P value
	n	%	n	%	
Fibrinogen >700 mg/dL	13	18.50	6	75.00	0.002 *
Procalcitonin >0.5 ng/mL	4	5.5	4	50	0.003 *
Blood Urea Nitrogen >22 mg/dL	5	6.90	4	50	0.004 *
RCP >150 mg/L	28	38.8	7	87.5	0.011 *
Neutrophils >80%	45	62.50	8	100	0.031 *
Leucocytes >10 10 ³ /μL	18	25.00	5	62.50	0.040 *
Urea >40 mg/dL	12	16.6	4	50	0.047 *

Table 2-B. The results show the association between laboratory parameters taken in the baseline, with the overall mortality. Analysis was performed with Fisher's exact test. * p-value < 0.05.

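### Day-3 SpO₂ >90% is scored without regard to the oxygen being delivered, and oxygen flow, a crude companion measure, is tested only within each arm

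*SAP*

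**What the plan says.** Protocol section 8.4 admits "Patients in need of supplemental O₂ with nasal prongs or mask-reservoir due to satO₂ <90% and respiratory distress". Oxygen need at entry is therefore universal, and at least two delivery devices are in use.

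SAP Item 15 puts flow and saturation on one line: "Delivered oxygen flow and maintenance of SpO₂ > 90%: will be analyzed at baseline and day three". It names no breathing condition, device or inspired oxygen fraction. The off-oxygen condition appears only in the day-40 list: "SpO2 without supplemental oxygen, use of home oxygen upon hospital discharge, days of supplemental oxygen use".

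SAP Item 26a lists the two as separate variables and promises comparison both within and between groups: "Administration of supplemental oxygen flow, oxygen saturation (spO₂), qSOFA scale, and gastrointestinal function will be assessed by comparing at baseline to day 3 intragroup and" (the quote stops just before the word for the between-group comparison). The Item 27 table does not carry this through:

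- Saturation above 90%: day 3 only, Fisher, between groups.
- Oxygen flow in litres: baseline against day 3, paired t test or Wilcoxon, within group only.

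Item 28 plans no method for missing data. Neither document says how a patient ventilated or dead by day 3 is scored on either row.

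**The concern.** Saturation on oxygen reflects both the patient's lungs and the support being given. If success is defined by saturation alone, a patient whose oxygen is increased and who then reads above 90% is a success, while a patient at exactly 90% on room air is a failure. The row cannot separate respiratory improvement from added support.

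Flow could supply the missing half, but Item 27 never joins the two. Equal litres through prongs and through a reservoir mask need not mean equal support, and a within-arm test cannot attribute a change to the supplement. Adjusting for baseline saturation alone would not cure this, because the day-3 reading would still be taken at whatever support the patient was on.

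At stake is how the day-3 respiratory rows are read, in particular the fall in flow flagged as significant in the intervention group.

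**Working it through.** **Inputs.** SAP Table 1-A, rows "Oxygen Saturation" and "Oxygen flow – L/min": baseline SpO₂ 92.73 ± 4.17 (control, CG) and 94 ± 3.18 (intervention, IG); baseline flow 5.9 ± 3.82 and 6 ± 3.29; n = 40 each. SAP Table 2-A, row "Oxygen Saturation >90% on day 3": 85% and 92.5% of 40, that is 34/40 and 37/40, p = 0.241. Same table, flow: CG 5.9 ± 3.8 to 6 ± 4.4 (p = 0.919); IG 6 ± 3.2 to 4.5 ± 3.5 (p = 0.014); no intergroup p-value.

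**1. The printed saturation result.** Fisher's exact test on 37/40 against 34/40 gives one-sided p = 0.2407, matching 0.241. The two-sided value is 0.481.

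**2. Was baseline SpO₂ read on oxygen?** Entry requires saturation below 90%. The baseline means exceed 90 by 2.73 and 4.00 points. The standard errors are 4.17/√40 = 0.659 and 3.18/√40 = 0.503, so the means lie 4.1 and 8.0 standard errors above 90, at mean flows of about 6 L/min. Readings on oxygen are the natural explanation.

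**3. Share already above the threshold at baseline.** Assume normality and compute P(SpO₂ > c) = 1 − Φ((c − mean)/SD), with c = 90 or, allowing for whole-number readings, 90.5.

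| | c = 90 | c = 90.5 |
|---|---|---|
| CG | 1 − Φ(−0.655) = 0.744 | 1 − Φ(−0.535) = 0.704 |
| IG | 1 − Φ(−1.258) = 0.896 | 1 − Φ(−1.101) = 0.864 |

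That is roughly 28-30 of 40 controls and 35-36 of 40 intervention patients.

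**4. Sensitivity of the Fisher row.** Suppose some day-3 successes were on more oxygen than at baseline and are recounted as failures. The true numbers are not printed, so these are scenarios (one-sided p):

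| Recounted | p |
|---|---|
| none | 0.241 |
| 4 CG, 0 IG | 0.033 |
| 4 CG, 4 IG | 0.293 |
| 0 CG, 4 IG | 0.727 |

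A few patients in either direction change the reading.

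**5. Flow between arms.** Day 3 alone: difference 6 − 4.5 = 1.5 L; SE = √((4.4² + 3.5²)/40) = 0.889; t = 1.687; p = 0.096 two-sided, about 0.048 one-sided. Change from baseline: (4.5 − 6) − (6 − 5.9) = −1.6 L. Its SE depends on the within-patient correlation r, which is not printed:

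| assumed r | SE | two-sided p |
|---|---|---|
| 0 | 1.186 | 0.177 |
| 0.3 | 0.994 | 0.108 |
| 0.5 | 0.842 | 0.057 |
| 0.7 | 0.656 | 0.015 |

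The within-IG p of 0.014 does not settle the comparison between arms.

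**6. Ventilated or dead by day 3.** The Figure 3 legend reports seven CG and three IG patients progressing to ventilation, without the days. Table 2-A prints n = 40 per arm on both rows. If any of these patients was ventilated by day 3, how that patient was scored cannot be recovered.

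**The case against.** The strongest reply is that flow and saturation were meant to be read together. Item 15 lists them on one line, and flow at a maintained saturation is a reasonable if crude index of oxygen need. The saturation row was not significant, so no positive claim rests on it. The SAP also has off-oxygen saturation and home-oxygen outcomes at day 40, and progression to intubation as a primary outcome. All of this stands, and it limits the consequence. It does not repair Item 27, where the rows are analysed apart and flow is not compared between arms.

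Several stronger readings are tempting but unsupported:

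- A reader might infer that the saturation criterion moves against oxygen need, because the estimated responder rate rises more in CG, where flow did not fall. Table 2-A does not show this. In IG flow fell and the responder rate did not; at day 3 IG has both the lower flow and the higher rate. The smaller IG rise reflects a higher start, and the baseline rates are approximations for a variable capped at 100.
- A reader might conclude that neither row measures lung function. The SAP does not claim that; its objective is clinical and biochemical change.
- A reader might extend the false-success problem to flow. Rising flow normally counts against the patient, unless the device changes or ventilation leaves flow unscored.
- A reader might suppose that staff aware of allocation set the flow. Item 19b has the research team giving the supplement and collecting data; nothing says that it adjusts oxygen.

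It is also fair that no passage says every day-3 reading was taken on oxygen. Some patients may have been weaned.

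**Conclusion.** The concern holds as a defect in the definition and analysis of two secondary outcomes. The day-3 saturation responder is not tied to delivered oxygen, so it can credit added support as success. Most patients probably met it at baseline: about 70-74% of CG and 86-90% of IG, if baseline saturation is roughly normal. Flow is pooled over devices and lacks the intergroup test that Item 26a promises. Patients ventilated or dead by day 3 have no scoring rule.

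How many day-3 successes were on more oxygen than at baseline cannot be determined, because saturation, flow and device are not printed jointly. The documents therefore show that misclassification is possible, not that it occurred or which arm it favoured. Mortality, survival and progression to intubation are unaffected. The change should be made, but the trial's main conclusion does not depend on it.

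**What to change.** Amend SAP Items 15, 26a and 27; nothing here concerns how oxygen is given.

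1. Define the day-3 responder as SpO₂ >90% at an oxygen flow no higher than the patient's own baseline flow. Count patients ventilated or dead by day 3 as non-responders.
2. Compare day-3 flow between arms with baseline flow as covariate, or by ranks with ventilated and dead patients ranked worst. Keep the within-arm tests as description only.
3. State for each SpO₂ reading whether it was on or off oxygen.
4. Where the device was recorded, use an ordinal support level (room air, prongs, reservoir mask, ventilation, death) as the comparison or as a sensitivity analysis. Where it was not, report litres with that limitation. Neither document plans a device record, so this step may not be possible.
5. Reconcile the timing: Items 15 and 26a give baseline and day 3 for saturation, Item 27 day 3 only.

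The SAP already prints results, so any re-analysis should be labelled post hoc and shown beside the existing rows.

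The cost is low. Steps 1 and 2 use saturation and flow already collected, plus ventilation and death dates needed for the primary outcomes. The downside is that a composite or rank outcome is less familiar than litres and still partly reflects how staff adjust oxygen.

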The energy balance of the supplements will be considered within the designated caloric balance for this group. The follow-up will be performed daily for 21 days or earlier, if they are discharged from hospital due to improvement in evolution or require access to the ICU, at which time the patient concludes the study. The following points will be supervised: 1. Application and consumption of the NSS supplementation as appropriate. 2. Recording of all the information in the records. 3. Food diaries of each patient. 4. Laboratory studies: QS every other day, BH every 3rd day, coagulation times every 3rd day, D-dimer and fibrinogen every 3rd day, serum electrolytes every other day, serum homocysteine every other day and serum 25 hydroxycholecalciferol levels every other day. 5. SpO2 %, heart rate, respiratory rate. 6. Clinical evaluation and record of bowel movements. 7. Taking of tricipital fold and arm

circumference, % muscle mass, % fat, BMI, weight, height every two days. 8. Days of hospital stay.

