2. To evaluate the effect of NSS on clinical and biochemical changes among patients.
3. To evaluate the effect of NSS on the biochemical status associated with overall mortality.

Study hypotheses

The null hypothesis: The nutritional support system will not reduce mortality or increase survival in patients with COVID-19 in stage III and comorbidities compared to conventional nutritional therapy.

Research hypothesis: The nutritional support system will reduce mortality and increase survival in patients with COVID-19 in stage III and comorbidities compared to conventional nutritional treatment.

Section 3: Trial Methods

9. Trial design - description of trial design

Item 9: Brief description of trial design including type of trial

Randomized, blinded, controlled clinical trial. Selected patients will be randomized into two groups: 1) Control Group (CG) will receive the hospital diet and 2) Intervention Group (IG) will receive the hospital diet and the NSS. Treatment allocation will have a 1:1 ratio.

10. Randomization

Randomization will be performed using a raffle; eighty numbers are to be placed (from 1 to 80). Subsequently, each number will be randomly selected from the raffle and sequentially assigned to one of the two groups, until reaching 40 numbers per group. Each number represents the moment the patient enrolls. In this way, once the recruitment starts, the first patient will be assigned number one; the second will be number two, and so on.

11. Sample size

Item 11: Full details of the same size calculation or alternatively reference to sample size calculation in protocol (instead of replication in SAP).

The sample size will be calculated using the formula: $n = \frac{z^2 p q}{e^2}$, where: 95% confidence level ($z = 1.96$), $p = 0.975$, $q = 0.025$, with a margin of error of 5% ($e = 0.05$), obtaining 38 patients per group for the sample.

12. Framework

Item 12: Superiority, equivalence or non-inferiority trial hypothesis testing framework, and wick comparisons will be presented on this basis.

The effect of NSS in increasing survival and reducing mortality in patients with COVID-19 will be demonstrated by the significant superiority of IG over CG.

13. Statistical Interim analyses and stopping guidance

Item 13a: Information on interim analyses specifying what interim analyses will be carried out and listing of time points:

No interim analyses are planned in the study.

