- Not meeting inclusion criteria including patients with respiratory rate disturbance (>30 bpm), glycemia >250 mg/dl, Glomerular filtration rate (GFR) < 60 ml/kg/m², platelets level (<150 10³ /L), concomitant autoimmune diseases (hypothyroidism, rheumatoid arthritis, atopic dermatitis), and/or respiratory disorders (bronchial asthma, obstructive sleep apnea syndrome, chronic lung lesions).
- Declined to participate.
- Randomization of all patients.
- Assignment of 40 patients to CG (received hospital diet and hospital treatment) and 40 patients to IG (received intervention - NSS, probiotics, B complex, hospital diet, and hospital treatment).

- Report of incidents.
- Variables analyzed in both groups with their evaluation periods.
- Primary outcomes.

24. Withdrawal/ Follow-up - level of withdrawal

Item 24a: Level of withdrawal e.g. from intervention and/or from follow up

The withdrawal levels that could be present in the study are listed as follows:

1. Participants can withdraw from the intervention and follow-up stops but the information collected is considered as data.
2. If patients decide to withdraw from follow-up, they are asked to allow us to use the data collected to date.
3. If a patient does not allow his/her data to be analyzed, they will not be considered in the analysis.
4. If the patient presents secondary reactions or does not adequately follow the treatment, they should leave the study and their data will be considered for the analysis.
5. Data from patients who die will be considered in the analysis.

Item 24b: Timing of withdrawal/lost to follow up data

The report of withdrawals and losses will be established in the CONSORT diagram, Kaplan-Meier curves, and primary outcomes section, where the timing of withdrawals will be mentioned, as well as the analysis and number of deaths.

Item 24c: Reasons and details of how withdrawal/lost to follow up data will be presented

Reasons for patients deciding to withdraw and deaths from COVID-19 complications will be presented on the CONSORT diagram, Kaplan-Meier curves, and in the primary outcomes section.

25. Baseline patient characteristics

Item 25a: List of baseline characteristics to be summarized

The clinical characteristics, demographic analysis and baseline values will be presented in tables. Details of the randomization will be mentioned in the methods section.

Item 25b: Details of how baseline characteristics will be descriptively summarized

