- Procalcitonin (ng / mL)

27. Analysis methods

To consider statistical significance in the results, a value of $p < 0.05$ will be used.

The analysis of the primary and secondary outcomes is shown in the following table.

Variable	Outcome	Timing	Normality test	Summary results	Parametric test	Nonparametric test	Categorical data test	Analysis type
Overall survival	Primary	40 days follow-up	-	Kaplan-Meier	-	-	Log Rank	Intergruppal
Progression to intubation	Primary	until the last patient is intubated	-	Kaplan-Meier	-	-	Log Rank	Intergruppal
Survival in intubated	Primary	40 days follow-up	-	Kaplan-Meier	-	-	Log Rank	Intergruppal
Oxygen flow (L)	Secondary	Basal vs day 3	Shapiro-Wilk	Mean and SD	Paired T test	Wilcoxon	-	Intragruppal
qSOFA (pts)	Secondary	Basal vs day 3	Shapiro-Wilk	Mean and SD	Paired T test	Wilcoxon	-	Intragruppal
Defecations per day (No.)	Secondary	Day 3	Shapiro-Wilk	Mean and SD	Unpaired T test	Mann Whitney	-	Intergruppal
Distension (Yes/No)	Secondary	Day 3	Shapiro-Wilk	Proportions	-	-	Fisher	Intergruppal
PHQ-9 (pts)	Secondary	Basal vs Discharge	Shapiro-Wilk	Mean and SD	Paired T test	Wilcoxon	-	Intragruppal
Oxygen saturation >90%	Secondary	Day 3	Shapiro-Wilk	Proportion	-	-	Fisher	Intergruppal
Hydric balance	Secondary	Day 3	Shapiro-Wilk	Mean and SD	Unpaired T test	Mann Whitney	-	Intergruppal
Bristol scale "normal"	Secondary	Day 3	Shapiro-Wilk	Proportion	-	-	Fisher	Intergruppal
Saturation without supplemental O2	Secondary	Day 40	Shapiro-Wilk	Mean and SD	Unpaired T test	Mann Whitney	-	Intergruppal
Need for supplemental O2 at home	Secondary	Day 40	Shapiro-Wilk	Proportion	-	-	Fisher	Intergruppal
Days of supplemental O2 use at home	Secondary	Day 40	Shapiro-Wilk	Mean and SD	Unpaired T test	Mann Whitney	-	Intergruppal
Postcovid syndrome	Secondary	Day 40	Shapiro-Wilk	Proportion	-	-	Fisher	Intergruppal
Decrease in weight	Secondary	Day 40	Shapiro-Wilk	Proportion	-	-	Fisher	Intergruppal
Gastrointestinal symptoms	Secondary	Day 40	Shapiro-Wilk	Proportion	-	-	Fisher	Intergruppal

28. Missing data

Item 28: Missing data-reporting and assumptions/statistical methods to handle missing data

(multiple imputation)

Statistical methods to handle missing data will not be performed.

30. Harms

Item 30: Sufficient detail provided on summarizing harms

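### qSOFA is tested only within each arm, on a floored score on which the intervention arm happened to start higher, so an intervention-only fall can appear with no treatment effect

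*SAP*

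**What the plan says.** Item 15 of the SAP sets the timing: "qSOFA scale: will be analyzed at baseline compared with day three". Item 26a says that the day-3 secondary outcomes, qSOFA among them, "will be assessed by comparing at baseline to day 3 intragroup and intergroup". The section 27 table carries out only half of that. Its row reads "qSOFA (pts) Secondary Basal vs day 3 Shapiro-Wilk Mean and SD Paired T test Wilcoxon - Intragruppal", and no row gives a between-arm test of qSOFA. Item 16 adds that "P values will be one-sided".

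The entry rules make low scores likely. The protocol (8.4, non-inclusion criteria) keeps out any patient "Who has criteria of sepsis or septic shock", and SAP Item 23 lists "patients with respiratory rate disturbance (>30 bpm" among the reasons for ineligibility. Neither document gives the range of the score, the number of patients at zero, or any way of handling a floor or a baseline difference.

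The SAP also prints results. Table 1-A gives baseline qSOFA as 0.425 ± 0.59 (control) and 0.65 ± 0.62 (intervention), p = 0.100. Table 2-A gives control 0.42 to 0.51 (p = 0.608) and intervention 0.65 to 0.43 (p = 0.040, starred). Its note describes an intergroup analysis, but the qSOFA row has no between-arm p-value.

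**The concern.** A significant fall in one arm beside a non-significant change in the other does not show that the arms differ. Here the weakness is sharper. The arm that starts higher tends to drift down through regression to the mean, and more of its patients have room to fall. The arm with more patients at zero can mostly only stay or rise.

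A reader of Table 2-A would take the starred result as an NSS benefit on clinical severity, under the SAP's secondary objective on clinical and biochemical changes. The planned test cannot separate that from the difference in starting level.

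**Working it through.** **Inputs.** Means, SDs and n = 40 per arm come from SAP Tables 1-A and 2-A; one-sided 5% comes from Item 16. Whole points from 0 to 3 is an assumption, because the documents say only points. The counts below do not depend on the maximum.

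**1. Reproduce the printed baseline p-value.** SE = √[(0.59² + 0.62²)/40] = √(0.7325/40) = 0.135. t = 0.225/0.135 = 1.66, two-sided p = 0.100, as printed. This is a two-sided value although Item 16 says one-sided; one-sided it would be 0.050.

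**2. Recover the baseline counts.** All distributions of 40 scores whose mean and sample SD round to the printed values were enumerated.

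| Arm | Patients at 0/1/2/3 | Mean | SD | At zero | Can fall |
|---|---|---|---|---|---|
| Control | 25/13/2/0 (only solution) | 17/40 = 0.425 | √[(21 − 17²/40)/39] = 0.594 | 62.5% | 15 |
| Intervention | 17/20/3/0 or 16/23/0/1 | 26/40 = 0.65 | √[(32 − 26²/40)/39] = 0.622 | 42.5% or 40% | 23 or 24 |

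The difference in the share at zero is itself within chance (Fisher two-sided p = 0.12 with 17 zeros, 0.07 with 16).

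**3. Split the printed difference in change.**
- Intervention: 0.43 − 0.65 = −0.22.
- Control: 0.51 − 0.425 = +0.085.
- Difference in change: −0.305, which is the day-3 gap (−0.08) minus the baseline gap (0.225).
- Share due to the baseline gap: 0.225/0.305 = 74%.

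**4. Compare the day-3 levels.** With n = 40 per arm, SE = √[(0.57² + 0.49²)/40] = 0.119, t = 0.08/0.119 = 0.67, two-sided p about 0.50.

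**5. How often the planned test misleads with no effect.** Both arms received the same assumed day-3 transitions, starting from the recovered counts (intervention 17/20/3). Score 0 moves to 1 with probability a; score 1 moves to 0 with probability r and to 2 with probability 0.05; score 2 moves to 0 with probability r/2 and to 1 with probability r. The test was a one-sided 5% signed-rank test within each arm, 4,000 runs per pattern.

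| a, r | Significant fall, control | Significant fall, intervention | Same test if an arm starts at 21/17/2 |
|---|---|---|---|
| 0.30, 0.30 | 0.2% | 8.4% | 1.4% |
| 0.30, 0.40 | 0.7% | 22.4% | 5.4% |
| 0.20, 0.30 | 1.5% | 21.4% | 7.3% |
| 0.25, 0.40 | 2.6% | 32.0% | 8.5% |
| 0.35, 0.50 | 0.9% | 34.3% | 7.3% |

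The last column uses a pooled starting distribution: two arms starting alike have the same rate. A separate simulation with other assumed transitions counted runs in which one arm alone fell significantly: about 7–14% for the intervention arm only, 0.3–1.6% for the control arm only.

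**6. Which between-arm test repairs it.** In that separate no-effect simulation, an unadjusted between-arm test of change rejected in about 14–18% of runs against a nominal 5%. Day-3 qSOFA adjusted for baseline rejected in 4–5%.

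**7. Check the printed day-3 values.** At n = 40 a control mean of 0.51 needs a total of 20.4 points; 20 points give 0.50 and 21 give 0.525. The intervention mean of 0.43 fits 17/40, but the smallest possible sample SD is then √[17 × 23/(40 × 39)] = 0.50, not 0.49. Dividing by n gives √(391/1600) = 0.49, but no intervention baseline distribution fits the printed SD with that divisor. Table 2-A's note says that deceased patients were excluded, which could leave 40 − 7 = 33 and 40 − 1 = 39, yet the row prints 40 and 40. With 33 and 39, the pooled SD is √[(32 × 0.57² + 38 × 0.49²)/70] = 0.528, t = 0.08/[0.528 × √(1/33 + 1/39)] = 0.64 and p is about 0.52, so step 4 barely moves.

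**The case against.** A reader might infer that the scale favours the intervention arm by construction. The documents do not support that. Both arms use the same scale and the same floor, and 40–42.5% of intervention patients also start at zero. The SAP states "Treatment allocation will have a 1:1 ratio" with random assignment, and the imbalance is compatible with chance and could have gone the other way.

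Nor is the floor the main cause. In a no-effect simulation of an unbounded normal score with the same baseline means, SD about 0.6 and an assumed baseline-to-day-3 correlation of 0.3–0.5, a fall in the intervention arm only appeared in 11–13% of runs and in the control arm only in 0.2–0.3%. Regression to the mean is enough.

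It is also tempting to say that no test could help because the limit lies in the scale. Step 6 shows otherwise: adjusting for baseline removes the excess false positives. It cannot reveal improvement in the 25 controls already at zero, but worsening in them can still be recorded and day-3 levels can still be compared.

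Finally, qSOFA is one of 14 secondary rows in section 27, and no primary conclusion rests on it. All of this stands. It narrows the point to the choice of test and leaves that point intact.

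**Conclusion.** The concern holds as a fault in the planned comparison. Item 26a and section 27 disagree, and the version that section 27 specifies can produce a significant fall in the intervention arm alone with no NSS effect. The rate is about 7–14% of runs in one set of simulations; the transitions tabulated above gave 8–34% for any significant intervention fall. These rates depend on assumed transitions and show direction and order of size only.

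The baseline counts rest on whole-point scoring from zero, and the day-3 comparison rests on printed values that do not fully fit n = 40. A reader might conclude that the printed p = 0.040 has been shown to be an artefact, or that the NSS has no effect on qSOFA. Neither follows. The within-arm p-values cannot be reproduced without the paired data, and a day-3 gap of 0.08 is inconclusive. What can be said is that the starred result is not evidence of a difference between arms. As a secondary outcome, this should be corrected but does not threaten the trial's main conclusion.

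**What to change.** - **Items 26a and 27:** replace the intragroup qSOFA test with a between-arm comparison of day-3 qSOFA, adjusted for or stratified by baseline score (for example an ordinal model or ANCOVA), so that the two items agree. Do not use an unadjusted between-arm test of change.
- **Tables 1-A and 2-A:** report the number of patients at each score by arm at baseline and day 3. Check the day-3 n and SDs, and state who was excluded.
- **Reporting:** do not star or cite the intervention-only fall as an NSS effect.

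Keep qSOFA as the outcome. Respiratory rate is recorded daily under the protocol ("SpO2 %, heart rate, respiratory rate"), but it is not an outcome in Items 15, 26a or 27. Substituting it, or an any-increase endpoint, after day-3 results have been printed would be a post-hoc change of outcome. The change of test is also late for the same reason and should be disclosed as such.

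The cost is SAP wording and one reanalysis of data already held. One starred secondary result is likely to be lost.
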